Given the toxicities of long term, continuous ADT, more contemporary hormonally-based treatment strategies utilizing intermittent ADT (IADT) and peripheral androgen blockade (PAB)have emerged for men with BCR [4-8].IADT, in which treatment with an LHRH agonist or antagonist is given in cycles consisting of "on" and "off" treatment phases, has been shown to lead to non-inferior overall survival and potentially improved quality of life in several prior phase 3 trials [4-8]. Though seemingly an improvement over continuous ADT with regards to preservation of overall quality of life, patients treated with IADT may experience delayed testosterone recovery during "off" treatment phases, and the percentage of time spent off treatment becomes progressively shorter with successive cycles of treatment, such that many patients are still at increased risk of long term metabolic derangements including osteoporosis, diabetes, and cardiovascular disease related to ADT[9].

Given the significant short- and long-term toxicities of castration-based therapy, which can impair quality of life and cause significant morbidity in this relatively asymptomatic population of men with BCR, there is an unmet medical need for well tolerated non-castrating therapies in this disease setting. Non-castrating therapies may ultimately be used to replace the need for ADT in biochemically relapsed disease, delay the initiation of ADT, or potentially lengthen the duration of "off" treatment phase as part of an intermittent ADT treatment strategy, therebyprolonging the time to development of castrate-resistant disease.

Various non-castrating agents have been tested in prior phase 2 clinical trials in the bichemically relapsed disease setting, including a prostatic acid phosphatase vaccine, GM-CSF, as well as other therapies such as imatinib, rosiglitazone,lenalidomide, celecoxib,and superoxide dismutase inhibitors including marimastatand ATN-224 [10-16]. In general, the clinical activity of these agents has been modest, withless than 5% of patients achievinga decline in serum PSA \geq 50% during protocol therapy with these non-castrating agents. In addition, several of the therapies were associated withappreciabletoxicity, including imatinib, which is especially undesirable in this population of patients without metastases and low disease burden. There exists a need for novel non-hormonal agents with improved biologic activity and better tolerabilityfor use in biochemically relapsed disease.

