The two most recent measurements of serum testosterone prior to Day 1 of protocol therapy must fulfill the following criteria:

- Both measurements are greater than 150 ng/dL.
- The two measurements are spaced at least 14 days apart.
- Both must be measured within 3 months of Day 1 of protocol therapy.
- There must not be an increase of > 50 ng/dL between these two successive measurements.
- 10. PSA doubling time (PSADT) ≤ 15 months, calculated based upon all serum PSA measurements obtained within 3 months prior to Day 1 of protocol therapy, witha minimum of three PSA measurements spaced at least 14 days apart (see section 6). PSA values obtained when serum testosterone was known to be less than 150 ng/dL, prior to local therapy, or within three months of last dose of LHRH agonist/antagonist or antiandrogen will be excluded from the calculation of the PSADT.PSADT calculation to be carried out using the following website:

http://nomograms.mskcc.org/Prostate/PsaDoublingTime.aspx

- 11. Total bilirubin less than 1.5 times upper limit of normal (ULN), or less than 3 times ULN at study entry in a patient with documented Gilbert"s disease.
- 12. ALT and AST levels less than 1.5 times ULN at study entry
- 13. Serum potassium greater than 3.5 mmol/L without oral supplementation
- 14. No history of uncontrolled hypertension (blood pressure > 160/100 mm Hg despite antihypertensive medication)
- 15. ECOG performance status of 0 or 1
- 16. Estimated life expectancy greater than 5 years
- 17. Age greater than or equal to 18 years at time of study entry
- 18. Ability to sign written informed consent

Phase II - Itraconazole

- 19. Ability to swallow study drug whole as a capsule
- 20. Primary prostate cancer tissue available for analysis is not required for inclusion onto this study but is strongly encouraged.
- 21. Patients who have partners of childbearing potential must be willing to use a method of birth control with adequate barrier protection as determined to be acceptable by the principal investigator and sponsor during the study and for 1 week after last study drug administration.

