The minimum PSA required for study entry varies depending on the modality of prior treatment, in keeping with guidelines set forth by the PSA Working Group [36]. In patients with prior radiation therapy (external beam or brachytherapy), the minimum PSA required for study entry is nadir PSA after RT + 2.0 ng/mL, consistent with ASTRO guidelines to define biochemical recurrence [40]. For patients with prior radical prostatectomy, definition of BCR varies by institution, but in general is usually defined as a PSA > 0.4 using a sensitive assay. A minimum PSA of 1.0 ng/mL is chosen for this study to allow for a more accurate determination of baseline

PSADT. For patients with prior ADT for biochemically relapsed disease, as outlined in section 1 of the protocol, there is no standard and commonly accepted definition of PSA progression. In prior clinical trials of intermittent ADT, widely varying PSA thresholds have been used as a "trigger" to re-initiate therapy, ranging from 2-20 ng/mL in absolute value or 25-100% of baseline or nadir PSA. The minimum PSA after prior ADT for BCR utilized in the current study (4.0 ng/mL or > 2 ng/mL above nadir PSA on prior ADT, whichever is higher) is acknowledged to be arbitrary but reflects current clinical practice and prior clinical trials of intermittent ADT, in which the second and subsequent cycles of ADT are often initiated upon reaching a pre-specified absolute PSA level that ranges from 2-20 ng/mL.

Patients with a history of prior androgen deprivation therapy will be required to have a stable serum testosterone level, as defined by the absence of an increase of more than 50 ng/dLbetween consecutive measurementsusing thetwo most recent measurements prior to the initiation of protocol therapy. A rising serum testosterone level may drive the rise in PSA during the period of testosterone recovery, which would then confound efforts to interpret pre-treatment vs. on-treatment changes in PSA doubling time and PSA kinetics, one of the secondary endpoints of the current study. Without attempting to exclude patients in the testosterone recovery phase, a lengthening of the PSA doubling time on therapy may be reflective of a plateau in testosterone recovery rather than a biologic effect of the therapeutic agent being tested.

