5.3.3 Correlative Endpoints

5.3.3.1 Endocrine Parameters

The mean change from baseline in serum androgen levels, including testosterone, DHEA-S, and androstenedione after 12 weeks of therapy with itraconazole will be determined to investigate further the mechanism of action of itraconazole in prostate cancer. Prior study in CRPC provided preliminary evidence that itraconazole, unlike the related azole compound ketoconazole, has a mechanism of action distinct from androgen synthesis inhibition [19], albeit in a castrate patient population. Demonstrating in the current study, with a non-castrate patient population, that itraconazoletherapy concurrently does not significantly impact serum androgen levels yet modulates serum PSA will lend further support to the hypothesis that itraconazole has a mechanism of action distinct from ketoconazoleand androgen synthesis inhibition. The main limitations of this particular analysis is that serum hormone levels may not reflect intra-tumoral androgen concentrations, and that this patient population is non-castrate with a different systemic hormonal milieu than the previous study in CRPC.

In the prior clinical trial of itraconazole in CRPC, there were several patients with a constellation of adverse events including hypokalemia, hypertension, and peripheral edema [19]. This constellation of symptoms has also occasionally been observed in prior studies of high dose itraconazole in patients with chronic fungal infections, and raises the possibility of induced mineralocorticoid excess. Serum aldosterone levels were measured in the prior study of itraconazole in CRPC (and were not elevated on therapy); however upstream compounds within

the adrenal synthetic pathway with mineralocorticoid activity, including deoxycorticosterone (DOC) and 11-deoxycortisol were not measured. A more comprehensive panel of adrenal and pituitary hormones, including ACTH, DOC, aldosterone, and 11-deoxycortisol, will be measured on a serial basis in the current study and the mean change from baseline will be determined.

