10.8.3 Analytic Plan for the Correlative Objectives

Endocrine Parameters

Serum hormone levels, including testosterone, androstenedione, DHEA-S, cortisol, aldosterone, 11-deoxycortisol, ACTH, and deoxycorticosterone, will be measured at baseline, at week 4, week 12, and at the time of PSA or clinical progression. To summarize the outcome, descriptive statistics including the mean percent change from baseline in serum hormone levels at 4 and 12 weeks will be presented with a standard deviation and Pearson"s correlation will be used to estimate the relationship between the baseline hormone level and percent change in hormone level after 4 and 12 weeks of treatment. Analysis of variance (ANOVA) methods for mixed models allowing for variable number of follow-up measurements with linear contrasts will be used to evaluate the change in serum hormone levels after 4 and 12 weeks of protocol therapy. It is hypothesized that approximately 15% of patients treated with protocol therapy will achieve a PSA decline \geq 50%. Depending upon the observed frequency, the ANOVA model will include a factor to test for the effect of PSA decline on change in serum hormone levels. Otherwise, analyses will compare the baseline and percent change in serum hormone levels at 4 and 12 weeks between patients achieving a PSA decline $\geq 50\%$ or not using a two group t statistic. For these exploratory analyses, graphic presentations will also be used to explore the overall pattern of change in serum hormone levels between those with and without a PSA decline.

Hedgehog Pathway

The quantitative expression of *GLI1*, a downstream product of the Hedgehog signal transduction pathway, will be measured by quantitative RT-PCR from serial skin biopsies obtained at baseline and after 4 weeks of therapy. The fold change in expression level after 4 weeks of protocol therapy will be calculated for each patient. Descriptive statistics will be used to summarize the proportion of patients with down-regulation of *GLI1* expression after 4 weeks of treatment with itraconazole. Down-regulation will be defined as any magnitude of decrease in *GLI1* mRNA expression after 4 weeks of protocol therapy compared to baseline expression level. The patient

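### Men still recovering testosterone after prior ADT can pass the stability rule, and the pooled testosterone change then understates any drug-induced fall

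*Combined protocol and SAP*

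**What the plan says.** Section 4.2 (item 9), repeated in Section 6.2.1 and in a footnote to the study schedule, sets four conditions on the last two testosterone values of a man with any prior ADT. Each value has to lie above 150 ng/dL. The gap between them has to be two weeks or longer. Neither may be older than 3 months when treatment starts. The fourth condition is the stability limit itself: "There must not be an increase of > 50 ng/dL between these two successive measurements".

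Section 4.2 also requires that the last LHRH dose ran out more than 3 months before entry. Section 5.1 explains the stability rule by reference to PSA doubling time (PSADT) only. Its worry is that, if nobody tried to keep out recovering men, "a lengthening of the PSA doubling time on therapy may be reflective of a plateau in testosterone recovery rather than a biologic effect". Section 1.1 acknowledges that "patients treated with IADT may experience delayed testosterone recovery during" the off-treatment phases, and Section 5.1 deliberately admits men in such a phase.

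For the androgen endpoints, Section 10.8.3 states that "descriptive statistics including the mean percent change from baseline in serum hormone levels at 4 and 12 weeks will be presented". It adds a mixed model over visits, in which the only between-patient factor mentioned is PSA decline, and a correlation of baseline level with percent change. Section 5.3.3.1 gives the use of the result: showing that treatment "does not significantly impact serum androgen levels yet modulates serum PSA will lend further support to the hypothesis" of a mechanism separate from androgen synthesis inhibition. Section 10.6 lists prior ADT and the time since its last dose among the baseline characteristics.

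**The concern.** The stability limit is scaled neither to the interval nor to the starting level. A man sampled twice in two weeks can be rising steeply and still count as stable, while a man who rises slightly more than the limit over nearly three months is excluded.

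For a man still recovering, testosterone would go up during the first 12 weeks without any drug. In a single-arm trial that drift is part of the measured change from baseline. The planned analysis has no term or stratum that separates drift from drug effect. The correlation of baseline level with percent change does not do so either, because regression to the mean gives the same pattern.

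The direction matters. Upward drift hides a fall, and absence of a fall is the finding that Sections 2.1 and 5.3.3.1 hope for. A larger sample would narrow the interval around the wrong value. For PSADT, a plateau in recovery during treatment would lengthen the doubling time and again look like drug benefit.

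**Working it through.** **Plan's own figures.** The documents give no calculation for the androgen endpoints. Their only design calculation is the two-stage test of PSA response in Section 10.2. An exact binomial calculation (continue if more than 2 of 22, reject at 8 or more of 40) gives power 0.803, one-sided alpha 0.040 and early-stopping probability 0.620, in line with the stated 80%, 0.05 cap and 0.62. Nothing below changes it.

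**Slopes that the rule accepts.** Inputs from Section 4.2: limit 50 ng/dL, minimum spacing 14 days, maximum about 3 months (taken as 91 days).

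- At 14 days: 50/14 × 28 = 100 ng/dL per 28 days.
- At 91 days: 50/91 × 28 = 15.4 ng/dL per 28 days.
- Ratio: 91/14 = 6.5.

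A man going from 151 to 201 ng/dL in 14 days (50/151 = 33%) qualifies. If that slope went on unchanged, he would be at 100/201 = +50% by week 4 and 300/201 = +149% by week 12. At 91-day spacing the same rise gives 15.4/201 = +8% and 46.2/201 = +23%. These are upper cases, since recovery may level off.

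**Effect on the pooled mean.** Let e be the true drug effect in every man, f the share of men recovering, and d their untreated percent rise by week 12. Then

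pooled mean = (1 − f)·e + f·[(1 + d)(1 + e) − 1] = e + f·d·(1 + e).

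The documents give none of e, f and d; all three are assumptions. With e = −20% this is −20% + 0.8·f·d:

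| Share recovering | Untreated rise 25% | 50% | 100% |
|---|---|---|---|
| 10% | −18% | −16% | −12% |
| 20% | −16% | −12% | −4% |
| 30% | −14% | −8% | +4% |
| 50% | −10% | 0% | +20% |

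For example, f = 0.3 and d = 0.5 give −0.20 + 0.8 × 0.15 = −0.08.

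**Share needed for full cancellation.** f = −e/[d(1 + e)] = 0.25/d for a 20% fall: 100% of men at a 25% rise, 50% at a 50% rise, 25% at a 100% rise. For a 10% fall, 0.10/(0.5 × 0.9) = 22% of men at a 50% rise.

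**Weighting.** Percent change gives low-baseline men more weight: a rise of 50 ng/dL is 25% from 200 ng/dL but 12.5% from 400.

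**Precision of an ADT-naive estimate.** With equal standard deviations, the standard error relative to all 40 men is √(40/30) = 1.15 if 30 are ADT-naive and √(40/20) = 1.41 if 20 are.

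**The case against.** The case for leaving the plan alone has real content.

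- **Safeguards.** The washout runs from expiry of the last dose, so a man on a 3-monthly depot must be more than 6 months past his last injection. Both values must exceed 150 ng/dL. PSA values taken at testosterone known to be below 150 ng/dL, or within three months of the last LHRH or antiandrogen dose, are left out of baseline PSADT. These reduce the number of recovering men, but none tests whether testosterone has stopped rising.
- **Unknown share.** A reader might infer that recovering men do enter in numbers and that a fall would be hidden. The documents support only that they can enter. With 20% of men rising 25%, a 20% fall still shows as −16%.
- **Role of the endpoint.** It is correlative, Section 5.3.3.1 uses measured language and lists limitations, and mechanism is not judged on testosterone alone. DHEA-S and androstenedione are also measured, and the ketoconazole contrast in Section 1.2.1 rests on adrenal androgens. This stands; nothing in the documents extends the concern to DHEA-S.
- **Baseline date.** A reader might infer from the schedule's testosterone row, placed under a 3-month window, that the percent-change baseline can be 3 months old. It cannot: that row carries the eligibility footnote, while Section 6.2.3 and the hormone-panel footnote put testosterone in the panel drawn within 28 days of Day 1.
- **Section 5.1.** It speaks only of an attempt to exclude recovering men. It does not say that the confounding has been removed.
- **Breadth of prior ADT.** The category includes remote (neo)adjuvant use in men who may be fully recovered. That is a reason to report these men by time since last dose, not to discard them.

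**Conclusion.** The point holds as a moderate weakness in a correlative analysis. The eligibility rule lets in men whose testosterone may still be rising, at rates that differ 6.5-fold with sampling interval, and the planned analysis cannot tell that rise from a drug effect. Any recovering share biases the pooled testosterone change upward, which favours the hoped-for conclusion.

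Under the assumed 20% fall with 20-30% of men recovering, the bias runs from 4 percentage points (a 25% rise in 20% of men) to 24 (a 100% rise in 30%). Attenuation is certain if any such men enter. Complete masking needs a large share or steep, continued recovery, and the documents do not show that either will occur. The change in PSADT is affected secondarily. The primary PSA endpoint, its sample size and its decision rule are outside this point.

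**What to change.** Change the analysis text:

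1. In Section 10.8.3, add prior ADT (yes/no) and its interaction with visit to the planned mixed model for testosterone. Use it to estimate the two trajectories; a non-significant interaction in 40 men should not be read as absence of recovery.
2. Report percent change in testosterone at weeks 4 and 12 separately for men with no prior ADT and men with prior ADT, the latter by time since last ADT. Remote adjuvant ADT is unlikely to matter, and this shows it.
3. Draw the statement about testosterone primarily from the ADT-naive estimate, with its confidence interval.
4. In Section 10.8.2, repeat the PSADT change in the same strata as a sensitivity analysis.

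The cost is precision: a standard error about 1.15 times the pooled one if 30 of 40 men are ADT-naive, and 1.41 times if 20 are, with equal standard deviations assumed. The data in Section 10.6 suffice, so no new samples are needed. No change to eligibility or the schedule is needed. Rewriting the limit as a rate would magnify ordinary assay variation over a 14-day gap, and the documents offer no basis for choosing a rate.

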4.3 Exclusion Criteria

- 1. Castrate-resistant disease, as evidenced by either:
 - Rising PSA on 2 consecutive measurements at least 2 weeks apart with concurrent documented serum testosterone < 50 ng/dL at the time of PSA measurement, or
 - Rising PSA on 2 consecutive measurements at least 2 weeks apart measured within 3 months after last LHRH agonist/antagonist injection
- 1. Prior bilateral orchiectomy
- 2. Congestive heart failure of NYHA class III or higher severity at study entry
- 3. History of chronic active hepatitis
- 4. Grade 2 or higher peripheral neuropathy at the time of study entry
- 5. Use of 5-alpha reductase antagonist (i.e. finasteride, dutasteride) or antiandrogen (i.e. flutamide, bicalutamide) within 6 weeks of Day 1 of protocol therapy
- 6. Use of systemic steroids at an equivalent dose of prednisone 5 mg/day or higher within 6 weeks of Day 1 of protocol therapy
- 7. Use of medications or herbal supplements which are known to potentially lower serum PSA within 6 weeks of Day 1 of protocol therapy (see appendix 1 for list of medications)
- 8. Use of other medications that may potentially interact with itraconazole within 1 week of study entry (see appendix 2 for list of medications)
- 9. Use of other investigational agents within 6 weeks of Day 1 of protocol therapy
- 10. Prior pathology consistent with small cell carcinoma or prostate cancer with predominantly neuroendocrine differentiation

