6.1 Study Schedule

	Pre-Study	Cycl	e 1	Cycle 2	Cycle 3	Cycle 4	Cycle 5 and beyond	End of Study
Procedure	Screening	Day 1	Day 8 (+/- 3 days)	Day 1 (+/- 7 days)	PSA or Clinical Progression			
Plasma/serum for banking (optional) ⁱ	Х			Х		Х		Х
PBMCs for banking (optional) ⁱ	Х							
Concomitant Medications	Х	Х	Х	Х	Х	Х	Х	
Serum sodium and potassium	Х		Х	Х	Х	Х	Х	
Archived primary prostate cancer tissue (optional) ^j	Х							
Itraconazole dispensed ^k		Х		Х	Х	Х	Х	
After Cycle 1								
Trough itraconazole& [OH]- itraconazole serum levels ¹				Х				

^a Informed Consent prior to any Screening procedures

Measured in same laboratory at each time point during study (if possible).

^c All serum PSA measurements within 3 months prior to Day 1 of protocol therapy will be included for the calculation of baseline PSA doubling time, with a minimum of three values each spaced at least 14 days apart.

^d Serum hormone levels should be collected between 8:00 am and 12:00pm if possible; will be shipped to UCSF and banked for later analyses; includes testosterone, cortisol, aldosterone, deoxycorticosterone, 11-deoxycortisol, adrenocorticotropic hormone (ACTH), dihydroepiandrostenedione-sulfate (DHEA-S), and androstenedione (see Appendix 3, section IV for processing, storage, and shipping instructions).

^e For serum testosterone measurement, if the patient does not have a history of ADT, a single measurement > 150 ng/dL within 3 months prior to Day 1 of protocol therapy will be required for study entry. For patients with any prior history of ADT, the two most recent serum testosterone measurements prior to Day 1 of protocol therapy must fulfill the following requirements:

- Both measurements > 150 ng/dL
- Both measurements obtained within 3 months prior to day 1 of protocol therapy
- Measurements must be spaced at least 14 days apart
- There must not be an increase of > 50 ng/dL between the two consecutive measurements
- ^f IV contrast with CT or MRI per individual investigator discretion. Whole body bone scan may consist of either technetium-99 labeled scan or sodium-fluoride PET bone scan.
- ^g May be omitted if completed within the past 30 days.
- ^h 3 mm punch biopsy non-scalp skin containing hair follicles

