6.2 Screening Period/Pre-Study Evaluation

All patients must sign a written informed consent form before study specific screening procedures are performed. Screening procedures to evaluate patient eligibility will be conducted as per the schedule outlined below. If the patient meets eligibility and screening requirements he will return to the site for the day 1 visit and drug dispensation.

6.2.1 Establish baseline PSA doubling time and serum testosterone levelfor eligibility determination (within 3 months prior to day 1 of protocol therapy)

- Estimation of baseline PSA doubling time
 - Calculated based upon all serum PSA measurements obtained within 3 months prior to day 1 of protocol therapy, with a minimum of three PSA measurements each spaced at least 14 days apart.
 - PSA values obtained when serum testosterone was known to be less than 150 ng/dL, prior to local therapy, or within three months of last dose of LHRH agonist/antagonist or antiandrogen will be excluded from the calculation of the PSA doubling time.
 - Measurement of all PSA values included in determination of PSA doubling time recommended to be performed in the same laboratory
 - Actual calculation of the PSA doubling time can be obtained from the following online calculator: http://nomograms.mskcc.org/Prostate/PsaDoublingTime.aspx
 - Patients eligible if PSA doubling time is less than or equal to 15 months.
- Serum testosterone level
 - If no prior androgen deprivation therapy:
 - A single measurement greater than 150 ng/dL within 3 months of day 1 of protocol therapy
 - If prior androgen deprivation therapy (either in adjuvant or biochemical relapse setting):

The two most recent measurements of serum testosterone prior to study entry must fulfill the following criteria:

- Both measurements greater than 150 ng/dL,
- The two measurements are spaced at least 14 days apart
- Both must be measured within 3 months of day 1 of protocol therapy
- There must not be an increase of > 50 ng/dL between these two successive measurements

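### Baseline PSA doubling time can read falsely short in a man who recently stopped a 5-alpha reductase inhibitor or other PSA-lowering agent, because the value-exclusion list omits these agents

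*Combined protocol and SAP*

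**What the plan says.** Three places set the doubling-time window. Section 4.2 (inclusion 10) has it "calculated based upon all serum PSA measurements obtained within 3 months prior to Day 1 of protocol therapy", with at least three values at least 14 days apart. Section 6.2.1 repeats this. Footnote c of the study schedule (Section 6.1) says "All serum PSA measurements within 3 months prior to Day 1 of protocol therapy will be included for the calculation of baseline PSA doubling time".

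The removal list appears in inclusion 10, where its drug-related part covers values "within three months of last dose of LHRH agonist/antagonist or antiandrogen will be excluded from the calculation", and again in Section 6.2.1, where it opens "PSA values obtained when serum testosterone was known to be less than 150 ng/dL, prior to local therapy, or within three months" and goes on to name LHRH agents and antiandrogens. Nothing else is removed.

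The washouts are in Section 4.3. The item numbered 5 bars "Use of 5-alpha reductase antagonist (i.e. finasteride, dutasteride) or antiandrogen (i.e. flutamide, bicalutamide) within 6 weeks of Day 1 of protocol therapy". The item numbered 7 bars "Use of medications or herbal supplements which are known to potentially lower serum PSA within 6 weeks of Day 1 of protocol therapy" and refers to Appendix 1 for the agents. Both periods are 6 weeks.

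The eligibility limit is a doubling time of 15 months or less. Section 5.1 explains that slower-doubling men are meant to be kept out. It also requires stable testosterone after prior ADT, so that a plateau in testosterone recovery is not mistaken for a drug effect on doubling time.

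**The concern.** The window is about 13 weeks and the washout is 6. A man who stopped a 5-alpha reductase inhibitor just over 6 weeks before Day 1 can have suppressed values early in the window and recovering or recovered values late in it. No rule removes the early values, and the requirement to use all values keeps them in. The fitted slope then mixes tumour growth with drug withdrawal.

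The plan treats the neighbouring cases differently. Antiandrogens share a sentence and a 6-week washout with 5-alpha reductase inhibitors, yet only antiandrogens carry a 3-month exclusion of PSA values. Section 5.1 guards against the same kind of artefact for testosterone, but a testosterone check is not designed to detect withdrawal of a PSA-lowering agent.

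Two things are at stake: correct application of the 15-month limit, and the secondary endpoint of mean percent change in doubling time. When the rebound ends, doubling time lengthens whether or not itraconazole does anything, and there is no control arm to show this.

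**Working it through.** The documents give no figure for this bias, so there is none to reproduce. What follows is an illustration.

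**Inputs from the documents.** Window of 3 months = 3 × 4.348 = 13.0 weeks; washout of 6 weeks; limit of 15 months; doubling time = ln 2 / slope of ln PSA on time (Section 10.8.2). I assume that the online calculator named for eligibility fits the same slope.

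**Assumptions.** PSA at weeks −12, −8, −4 and 0 (the last just before treatment); last dose at week −6, the limiting case; PSA multiplied by (1 − s) while on the agent, with s from 10% to 30%. There are three recovery shapes: immediate; log-linear, complete at week 0; and exponential with a 4-week half-time.

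**Formula.** The times centred on their mean are −6, −2, 2 and 6, with sum of squares 80. The fitted slope is the true slope plus the sum of (centred time × log suppression) divided by 80. For a true 24 months, the true slope is 0.6931 / (24 × 4.348) = 0.00664 per week.

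**Example, s = 10%, immediate recovery.** ln 0.9 = −0.1054 applies at weeks −12 and −8. The added slope is (6 + 2) × 0.1054 / 80 = 0.01054. The total is 0.01718, and 0.6931 / 0.01718 = 40.3 weeks = 9.3 months.

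**Example, s = 10%, 4-week half-time.** The log suppression is −0.1054, −0.1054, −0.0733 and −0.0360. The added slope is (0.8429 − 0.1467 − 0.2160) / 80 = 0.00600. The total is 0.01265, which gives 12.6 months.

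Apparent doubling time (months) for a true 24 months:

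| Recovery | s = 10% | s = 20% | s = 30% |
|---|---|---|---|
| Immediate | 9.3 | 5.5 | 3.8 |
| Log-linear to week 0 | 10.3 | 6.3 | 4.4 |
| Half-time 4 weeks | 12.6 | 8.1 | 5.7 |

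All are below 15. With immediate recovery, suppression of about 4% is enough to bring a true 24 months under the limit. At 5% suppression with a 4-week half-time the reading is 16.7 months, so the limit still holds there.

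**Where there is no bias.** If all three values are on a stable dose (weeks −12, −10, −8), or all follow full recovery (weeks −4, −2, 0 with immediate recovery), the fit returns 24.0 months.

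**Secondary endpoint.** Take a true 12 months, recovery complete by Day 1, an inert drug, and on-treatment values that show the true rate. At 10% to 30% suppression the baseline reads 6.7 to 3.3 months (immediate) or 7.2 to 3.7 months (log-linear). The apparent change, 12 / baseline − 1 before rounding, is +79% to +268% or +66% to +224%. If 40 men contribute, each such man moves the mean by between 66/40 = 1.7 and 268/40 = 6.7 percentage points.

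**Would a 6-week exclusion after the last dose be enough?** Take three retained values at 6, 8 and 10 weeks after the last dose, a true 24 months and a 4-week half-time. For three equally spaced values the slope is (last − first) / 4. At s = 10%, log suppression goes from −0.0360 to −0.0178, adding 0.0182 / 4 = 0.00454. The total is 0.01118, or 14.3 months. At 20% and 30% the readings are 10.0 and 7.6 months. A 6-week period removes the bias only if PSA has recovered by then.

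**The case against.** The strongest reply is about reach. The bias needs a man who used such an agent in the window, stopped it more than 6 weeks before Day 1, and has values on both sides of the stop or during recovery. Nothing in the documents shows how many men fit that, or that any do. This stands, and it limits the point to what the rule can do.

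A second reply is that the suppression range is assumed. For the agents in exclusion 7, the protocol says only "which are known to potentially lower serum PSA within 6 weeks of Day 1 of protocol therapy". It supports no particular percentage for a supplement such as saw palmetto or pomegranate. This also stands: the table shows sensitivity to s and does not describe any named agent.

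A third reply is that change in doubling time is secondary, mostly descriptive, and already acknowledged as fragile in Section 1.3.3. That lowers the priority. However, Section 10.8.2 also plans a paired test of the change, and fragility is no reason to leave in a source of error that has a known direction.

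A reader might infer that the primary result is compromised. The documents do not support that. The primary endpoint is a confirmed PSA fall of at least 50% from baseline. Recovery raises PSA, and a later plateau is not a 50% fall, so the rebound cannot create responders. The two-stage decision rule and sample size do not use doubling time.

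**Conclusion.** The point holds as a gap in the doubling-time rule. The text requires on-agent values to be included, the washout is shorter than the window, and the direction of the error is clear when values straddle the stop or the recovery. For an affected man the error can be large: a true 24 months reads about 9 to 13 months at 10% suppression and about 4 to 6 months at 30%, over the recovery shapes tried. These sizes rest on assumed suppression, recovery and sampling times. The effect on the trial as a whole cannot be estimated, because the number of men affected is unknown.

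It would go too far to say that the rule makes baseline doubling time falsely short in general, or that the 6-week washout is itself wrong. The first is untrue when values do not straddle the change. The second is a clinical question that this review does not judge. The finding is that the value-exclusion list and the washouts do not match.

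**What to change.** Reconcile the value-exclusion list with exclusions 5 and 7. Add to inclusion 10, Section 6.2.1 and schedule footnote c that PSA values obtained while taking a 5-alpha reductase inhibitor or a named PSA-lowering agent, or within a stated period after its last dose, are left out of the doubling-time calculation.

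Two details matter:

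- **Name the agents.** Appendix 1 is a single list that also contains interaction drugs such as midazolam, methadone and simvastatin. Citing all of it could void valid PSA values.
- **State the post-dose period.** Reconcile it with both the 3-month value exclusion already used for antiandrogens and the 6-week washout, and give the recovery assumption behind it. As shown above, a 6-week period works only if PSA has recovered by then.

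The cost is a short agent list and one sentence in three places. A few men would wait some weeks to collect three valid values; three values 14 days apart span 28 days. Treatment, sample size and the primary analysis do not change. This is a cheap improvement.
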